6.1.6. Pooling of Sites

Not applicable; sites are pooled into regions as part of randomization stratification.

6.1.7. Derived Variables

- **Day 1** = first day of Treatment Period 1, where either dasiglucagon is first initiated (dasiglucagon + SOC treatment group) or date of randomization (SOC only treatment group). Study day will be calculated with respect to Day 1.
- **Study Week** = a 7- or 21-day period derived for displays of events related to CGM and/or SMPG results, gastric carbohydrate administrations, health care outcomes, and other assessments that may occur between clinic visits where a defined study week is needed. The study weeks will be derived as follows:

Study Week	Planned Days	Analysis Start Date	Analysis Stop Date
Baseline	Days -14 – -1	Analysis Stop Date – 13 days	Day 1 visit date – 1 day
Week 1 *	Days 1 – 7	Day 1 visit date	Week 5 visit date – 22 days
Week 2	Days 8 – 14	Analysis Stop Date – 6 days	Week 5 visit date – 15 days
Week 3	Day 15 – 21	Analysis Stop Date – 6 days	Week 5 visit date – 8 days
Week 4	Days 22 – 28	Analysis Stop Date – 6 days	Week 5 visit date – 1 day
Weeks 2-4	Days 8 – 28	Same as Week 2 Analysis Start Date	Week 5 visit date – 1 day
Week 5 *	Days 29 – 35	Week 5 visit date	Week 9 visit date – 22 days
Week 6	Days 36 – 42	Analysis Stop Date – 6 days	Week 9 visit date – 15 days
Week 7	Days 43 – 49	Analysis Stop Date – 6 days	Week 9 visit date – 8 days
Week 8	Days 50 – 56	Analysis Stop Date – 6 days	Week 9 visit date – 1 day
Weeks 6-8	Days 36 – 56	Same as Week 6 Analysis Start Date	Week 9 visit date – 1 day

Study Week	Planned Days	Analysis Start Date	Analysis Stop Date
------------	--------------	---------------------	--------------------

* This might end up being more or less than 7 days if the Week 5 visit day is not exactly at Day 29 or if the Week 9 visit day is not exactly at Day 57; both Week 5 and Week 9 visits have a \pm 2 day visit window.

No overlap in days between study weeks is allowed, except in cases where a multiple-week period is indicated. If there is overlap, the earlier week is favored. In case of early termination before a subject reached the end of the respective period (Week 5 or Week 9), the derivation for the weeks will be based on the planned day up to date of discontinuation (where any week after date of discontinuation will be set to missing), as follows:

Study Week	Planned Days	Analysis Start Date	Analysis Stop Date
If subject discontinues trial before reaching Week 5:			
Week 1	Days 1 – 7	Day 1 date	Earliest of Analysis Start Date + 6 days, or date of trial discontinuation
If subject discontinues trial before reaching Week 9:			
Week 2	Days 8 – 14	Date 1 date + 7 days	Earliest of Analysis Start Date + 6 days, or date of trial discontinuation
Week 3	Day 15 – 21	Date 1 date + 14 days	Earliest of Analysis Start Date + 6 days, or date of trial discontinuation
Week 4	Days 22 – 28	Date 1 date + 21 days	Earliest of Analysis Start Date + 6 days, or date of trial discontinuation
Weeks 2-4	Days 8 – 28	Same as Week 2 Analysis Start Date	Same as latest of Week 2, Week 3, or Week 4 Analysis Stop Date
Week 5	Days 29 – 35	Week 5 date	Earliest of Analysis Start Date + 6 days, or date of trial discontinuation
Week 6	Days 36 – 42	Week 5 date + 7 days	Earliest of Analysis Start Date + 6 days, or date of trial discontinuation

Study Week	Planned Days	Analysis Start Date	Analysis Stop Date
Week 7	Days 43 – 49	Week 5 date + 14 days	Earliest of Analysis Start Date + 6 days, or date of trial discontinuation
Week 8	Days 50 – 56	Week 5 date + 21 days	Earliest of Analysis Start Date + 6 days, or date of trial discontinuation
Weeks 6-8	Days 36 – 56	Same as Week 6 Analysis Start Date	Same as latest of Week 6, Week 7, or Week 8 Analysis Stop Date

- **Study Visit** = in-clinic visit as per the schedule of events, to be used for assessments that can only occur during a clinic visits (e.g., PedsQL, safety assessments like clinical laboratory assessments and vital signs).
- **Change from baseline** = value at current time point – value at baseline.
- **TEAE** = an AE with an onset at the time of or following the start of treatment with the trial drug (dasiglucagon + SOC arm) or date/time of randomization (SOC only arm) through the Follow-up visit or Early Termination visit, whichever occurs first.
- **PK Clearance:**

$$CL/f \text{ (L/h)} = R_0/C_{ss}$$

where R_0 = infusion rate (pmol/h) and C_{ss} = concentration at steady state (pmol/L), weight ($1\mu\text{g/kg/hr} = 295.7 \text{ nmol/kg/h}$)

- **SMPG-detected Hypoglycemia episode** = PG <70 mg/dL or 3.9 mmol/L, as detected by SMPG and reported in the eCRF. A single hypoglycemia episode is defined as up until 60 minutes from the start of the episode even if normoglycemia (>70 mg/dL) is not reached within this time. A new episode of hypoglycemia is to be reported when the next PG value below 70 mg/dL (3.9 mmol/L) is measured. Episodes are defined as the ones entered in the eCRF, no statistical programming will be done to define an episode.
- **Clinically significant SMPG-detected hypoglycemia episode = defined as SMPG-detected Hypoglycemia episode with any PG <54 mg/dL during the episode, (value reported in the hypoglycemic event form)..**
- **CGM-detected hypoglycemia episode** = PG <70 mg/dL (3.9 mmol/L) for 15 minutes or more, as measured by CGM. A single hypoglycemia episode is defined as up until 60 minutes from the start of the episode even if normoglycemia (>70 mg/dL) is not reached within this time. A new episode of hypoglycemia is to be reported when the next PG

value below 70 mg/dL (3.9 mmol/L) is measured. Episodes are defined by programming using external CGM data.

- **Clinically significant CGM-detected hypoglycemia episode** = PG <54 mg/dL or 3.0 mmol/L for 15 minutes or more, as detected by CGM. A single clinically significant hypoglycemia episode is defined as up until 60 minutes from the start of the episode even if normoglycemia (>54 mg/dL) is not reached within this time. A new episode of clinically significant hypoglycemia is to be reported when the next PG value below 54 mg/dL (3.0 mmol/L) is measured. Episodes are defined by programming using external CGM data.
- **Event rate** = average of the weekly number (sum) of events/episodes, based on the number of weeks in the relevant period (Baseline, Week 2-4, or Week 6-8). Events include hypoglycemia, clinically significant hypoglycemia, gastric carbohydrate administrations, and SMPG readings.
- **Number of weeks** = number of days in a relevant period (Baseline, Treatment Period 1, Week 2-4, Treatment Period 2, or Week 6-8) divided by 7. If a subject discontinues during a week, then a partial week will be calculated.
- **Percent time (CGM)** = (number of minutes where PG at a pre-defined level / total number of minutes patient is wearing CGM) * 100%. For this calculation, one assessment of CGM will be considered having a 5 minutes duration. The possible levels are:
 - **In range:** PG between 70-180 mg/dL (3.9-10.0 mmol/L), inclusive
 - **Hypoglycemia:** PG <70 mg/dL (3.09 mmol/L)
 - **Clinically significant hypoglycemia:** PG <54 mg/dL (3.0 mmol/L)
- **Time to hypoglycemia** = time from beginning of meal to the beginning of the first continuous 15-minute CGM reading of PG <70 mg/dL.
- **Extent of hypoglycemia (AOC_{glucose})** =

$$\sum_{k=0}^{X-1} \frac{(UL - PG_k) + (UL - PG_{k+1})}{2} \times (t_{k+1} - t_k)$$

where UL is the upper limit for the hypoglycemia definition (70 mg/dL or 54 mg/dL); k is the k^{th} time point that glucose is measured using CGM; PG_k is the PG value in mg/dL on the k^{th} time point; and X is the end time point of the 3-week treatment period (Weeks 2-4). When $k = 0$, t_k is set to 0 and PG_k is the PG value corresponding to the start of the 3-week treatment period. Only PG values less than UL will be included in the calculation. If $PG \geq UL$ at the k^{th} time point and $PG < UL$ at the $k^{\text{th}}+1$ time point, then the extent of hypoglycemia for that interval will be determined as follows:

1. Estimate time point on x-axis where $PG = UL - 0.01$ (for values measures in mmol/L), as if a straight line were drawn between time points by using the following formula:

$$\hat{k} = \frac{(UL - 0.01) - b}{m}$$

Where b = y-intercept of line created by the coordinates (k^{th} time point, PG_k) and ($k^{\text{th}}+1$ time point, PG_{k+1}) and m = slope of that line.

2. Substituting PG_k with UL and t_k with $t_{\hat{k}}$, the formula for the estimated interval below UL is as follows:

$$\frac{(UL - UL) + (UL - PG_{k+1})}{2} \times (t_{k+1} - t_{\hat{k}})$$

Similar methodology would be utilized if $PG < UL$ at the k^{th} time point and $PG \geq UL$ at the $k^{\text{th}}+1$ time point, with the estimate of the time point where PG crosses the UL threshhold being estimated for $t_{\hat{k}+1}$.

If the time period between two timepoints is greater than 1 hour then no area will be calculated over this timeperiod.

If PG results from the k^{th} time point are missing, then $k-1$ scores will be used and the weight will be $t_{k+1}-t_{k-1}$.

The extent of hypoglycemia calculated as above will then be divided by the total duration of CGM assessments calculating as summing all $t_{k+1} - t_k$ duration used in previous formulae. Time points for which $PG > UL$ will be included in the total duration. This variable will then be used the endpoint evaluation.

- **Nightly gastric carbohydrates** = amount of gastric carbohydrates (g) given between midnight and 6 am, inclusive.
- **Amount of [variable]** = average of the weekly amount of [variable] in the relevant period (Baseline, Week 2-4, and/or Week 6-8). Variables include total amount of gastric carbohydrates administered (via NG tube or gastrostomy) to treat hypoglycemia, nightly gastric carbohydrates administered, total amount of gastric carbohydrates administered, and number of IV glucose infusions to treat hypoglycemia.
- **PedsQL scoring for each scale and summary score⁸:**
 - Step 1: Transform score - items are reversed scored and linearly transformed to a 0-100 scale as follows: 0=100, 1=75, 2=50, 3=25, and 4=0 so that higher scores indicate better health-related quality of life (QoL) (less negative impact).

- Step 2: Calculate scores - computed as the sum of the items divided by the number of items answered (this accounts for missing data). If more than 50% of the items in the scale are missing, the scale score is not computed.
- **PedsQL Physical Functioning scale score** = average of transformed physical functioning scale items; up to 6 items for infants (1-12 months), 9 items for infants (13-24 months), and 8 items for toddlers, young children, children, and teens.
- **PedsQL Emotional Functioning scale score** = average of the transformed emotional functioning scale items; up to 12 items for infants (1-12 months) and infants (13-24 months) and 5 items for toddlers, young children, children, and teens.
- **PedsQL Social Functioning scale score** = average of the transformed social functioning scale items; up to 4 items for infants (1-12 months) and 5 items for infants (13-24 months), toddlers, young children, children, and teens.
- **PedsQL School Functioning scale score** = average of the transformed school functioning scale items; up to 3 items for toddler and 5 items for young children, children, and teens. This scale was not collected for infants (1-12 months) or infants (13-24 months).
- **PedsQL Physical Symptoms scale score** = average of the transformed physical symptoms scale items; up to 10 items for infants (1-12 months) and infants (13-24 months). This scale was not collected for toddlers, young children, children, or teens.
- **PedsQL Cognitive Functioning scale score** = average of the transformed cognitive functioning scale items; up to 4 items for infants (1-12 months) and 9 items for infants (13-24 months). This scale was not collected for toddlers, young children, children, or teens.
- **PedsQL Physical Health summary score** = average of the transformed physical functioning scale items and physical symptoms scale items (infants [1-12 months] and infants [13-24 months] only).
- **PedsQL Psychosocial Health summary score** = average of the transformed emotional functioning scale items, social functioning scale items, school functioning scale items (toddlers, young children, children, and teens only), and cognitive functioning scale items (infants [1-12 months] and infants [13-24 months] only).
- **PedsQL Total scale score** = average of the transformed physical functioning scale items, emotional functioning scale items, social functioning scale items, school functioning scale items (toddlers, young children, children, and teens only), physical symptoms scale items (infants [1-12 months] and infants [13-24 months] only), and cognitive functioning scale items (infants [1-12 months] and infants [13-24 months] only).
- **Fasting Tolerance start and end dates**

Fasting Tolerance start date/time is defined as per e-CRF fields: Meal start date, start time

Fasting Tolerance end date/time is defined as the earliest between:

-e-CRF end date, end time

- first continuous 15-minute CGM reading of <70 mg/dL (3.9 mmol/L) from external CGM data. As CGM assessment is not exactly done every 5 minutes it will require at least 2 CGM evaluation < 70mg/dL no separated more than 10 minutes and no CGM value > 70mg/dL during this 15 minutes time period.

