5.3. Dasiglucagon for the Treatment of Congenital Hyperinsulinism

5.3.1. Dasiglucagon

Dasiglucagon is a peptide analog of human glucagon that is in development for the treatment and prevention of hypoglycemia in patients with diabetes mellitus and CHI via SC or intramuscular (IM) administration. Dasiglucagon is a stable analog of glucagon that has been specifically designed to overcome the issues with fibril formation and instability in solution observed with marketed glucagon products. Compared to native human glucagon, dasiglucagon also comprises 29 amino acids. As a result of chemical modifications (7 amino acid substitutions compared to human glucagon), the pronounced tendency of glucagon to form fibrils and aggregate has been effectively prevented in dasiglucagon. In addition, the chemical stability in aqueous media at physiological pH has been improved.

To support the use of dasiglucagon in the pump, compatibility/in-use studies have been performed with dasiglucagon 4 mg/mL in the Roche Accu-Chek® Combo pump using the Accu-Chek® Spirit 3.15 mL cartridge system and the Accu-Chek® FlexLink infusion set. The studies support an in-use time for up to 6 days at 37°C.

Dasiglucagon was granted orphan drug designation by the European Commission on 20 June 2017 for the 'treatment of congenital hyperinsulinism.' Furthermore, the FDA granted an orphan drug designation for the 'treatment of hypoglycemia in patients with congenital hyperinsulinism (CHI)' on 10 August 2017.

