7.4. Exposure and Compliance

Study drug administration will be summarized separately for total dasiglucagon exposure ($\mu\text{g}/\text{kg}$) and total duration of exposure (days), respectively, for each treatment period. The total dasiglucagon exposure will also be described by study week. Additionally, the infusion rate, defined as the average hourly weight-adjusted infusion rate over the last 7 days of the respective treatment period (i.e., $\mu\text{g}/\text{kg}/\text{hr}$ and $\mu\text{g}/\text{hr}$), will be summarized for each treatment period and each study week.

8. Efficacy Analysis

The FAS and PP Set will be used to summarize efficacy data. The PP Set will be used only as supportive analysis. Patients will be analyzed by treatment period according to the planned treatment group (SOC and dasiglucagon + SOC for Treatment Period 1 and dasiglucagon + SOC for Treatment Period 2).

The efficacy analysis will be separated into 3 categories:

1. Treatment Period 1, FAS
2. Treatment Period 1, PP (primary and key secondary endpoints only)
3. Treatment Period 2, FAS

Efficacy Procedures

Plasma Glucose Monitoring: During the study, SMPG assessments will be performed regularly (at least 3 times daily, preferably before meals) to evaluate efficacy. At each visit, the investigator will check for patient compliance in number of daily SMPG measurements and that hypoglycemia episodes are recorded in the diary.

Continuous Glucose Monitoring: CGM will be used in a blinded manner to evaluate efficacy in terms of hypoglycemia episodes. The CGM is required for the 2 weeks up to randomization, during Week 2-4 of Treatment Period 1, and during Week 6-8 of Treatment Period 2. However, short pauses of 1-3 days due to skin irritation or discomfort are allowed after consultation with the investigator.

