11.1. Pharmacokinetic Analysis

Plasma concentrations are collected on week 6 and week 9 as per Schedule of Events [Table 2](#). Descriptive summaries will be presented for plasma PK concentrations by study visit and infusion rate (in $\mu\text{g}/\text{kg}/\text{hr}$) at the end of Treatment Period 2, as described in Section [7.4](#). Information pertaining to PK data collection will be listed.

PK analysis is performed using PK population according to actual treatment received.

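### The SAP's clearance formula works in pmol but prints its mass-to-molar conversion in nmol, so any CL/f derived from the printed unit is 1000 times too large

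*SAP*

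**What the plan says.** SAP 6.1.7 (Derived Variables, PK Clearance) defines apparent clearance in L/h as the infusion rate divided by the steady-state concentration. The units are fixed as follows: "R_0 = infusion rate (pmol/h) and C_{ss} = concentration at steady state (pmol/L"). After these definitions the line carries the bare word for weight ("concentration at steady state (pmol/L), weight"), followed by a bracketed conversion that equates 1 µg/kg/hr with "295.7 \text{ nmol/kg/h".

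Three other places bear on this:

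- **Protocol 5.3.1** gives the size of the molecule: "Compared to native human glucagon, dasiglucagon also comprises 29 amino acids". Neither document states a molecular weight.
- **SAP 7.4** describes the infusion rate that would feed the formula as the "average hourly weight-adjusted infusion rate over the last 7 days of the respective treatment period", and gives it in both µg/kg/hr and µg/hr.
- **SAP 11.1** sets out the PK reporting: "Descriptive summaries will be presented for plasma PK concentrations by study visit and infusion rate". Clearance is not named there.

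**The concern.** The formula gives L/h only if R0 and Css use the same molar unit, and the SAP chose pmol for both. The one conversion supplied to get from the recorded mass rate to that molar rate is printed in nmol. A programmer who follows it literally gets nmol/kg/h, multiplies by 1000 to reach pmol, and inflates R0 and therefore CL/f by that factor.

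The conversion is also per kilogram, whereas R0 is not. Body weight is mentioned without any operation attached to it. Someone who starts from the µg/kg/hr rate used in SAP 11.1 and does not multiply by weight gets L/h/kg under an L/h label.

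What is at stake is any clearance value taken from this definition into a report. SAP section 1 allows its planned analyses to enter study reports, submissions or manuscripts. Protocol 9.7 says that no pediatric PK data existed for dasiglucagon, so the documents hold no pediatric clearance value against which a wrong result would stand out.

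**Working it through.** **Inputs.** From SAP 6.1.7: CL/f = R0/Css, R0 in pmol/h, Css in pmol/L, and the printed factor 295.7 nmol per µg. From Protocol 5.3.1: 29 residues. From SAP 3.4: infusion rates of 10 to 70 µg/h. The documents give no molecular weight and no Css.

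**Step 1: does the printed equality hold?** Implied molar mass = mass / amount.

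| Reading of 295.7 | Calculation | Molar mass | Per residue (÷ 29) |
|---|---|---|---|
| nmol (as printed) | 1e-6 g / 295.7e-9 mol | 3.38 g/mol | 0.117 g/mol |
| pmol | 1e-6 g / 295.7e-12 mol | 3,381.8 g/mol | 116.6 g/mol |

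The printed reading puts each amino acid below the mass of one hydrogen atom, so the plan's own figure does not reproduce.

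**Step 2: is pmol the only prefix that fits?** Assume residue masses from 57.05 to 186.21 g/mol, plus one water (18.02).

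- Lower bound: 29 × 57.05 + 18.02 = 1,672 g/mol, so 1 µg = 598 pmol.
- Upper bound: 29 × 186.21 + 18.02 = 5,418 g/mol, so 1 µg = 185 pmol.

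One microgram is therefore 185 to 598 pmol, or 0.18 to 0.60 nmol. The number 295.7 lies in that range only as pmol.

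**Step 3: effect on R0.**

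| Rate | R0 with pmol | R0 with the printed nmol converted to pmol |
|---|---|---|
| 10 µg/h | 10 × 295.7 = 2,957 pmol/h | 2,957,000 pmol/h |
| 70 µg/h | 70 × 295.7 = 20,699 pmol/h | 20,699,000 pmol/h |

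**Step 4: effect on CL/f.** Css cancels from the ratio, so the error is exactly 1000-fold at any concentration. To show the scale at 70 µg/h, with Css assumed to lie between 300 and 10,000 pmol/L:

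- with pmol: 20,699/300 = 69.0 L/h, down to 20,699/10,000 = 2.07 L/h;
- with the printed unit: 20,699,000/300 = 68,997 L/h, down to 20,699,000/10,000 = 2,070 L/h.

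**Step 5: the weight term.** For an assumed 10 kg child on 70 µg/h, the per-kg rate is 7 µg/kg/hr. Then 7 × 295.7 × 10 = 20,699 pmol/h, the same as 70 × 295.7. Both routes agree once the multiplication by weight is written down. Without it, the per-kg route gives 7 × 295.7 = 2,069.9, too small by the child's weight in kg.

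**The case against.** The strongest objection is reach. SAP 11.1 plans summaries of concentrations, SAP 2.2.3 describes only two samples for drug levels, and no visible section plans a clearance table or listing. A wrong factor in a variable that may never be derived is close to an editorial slip. This stands in part. It limits the consequence, but the SAP does define clearance as a derived variable, and a definition in a programming specification should work as written. The table shells are not available, so its use elsewhere cannot be checked.

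The harm also needs a chain: someone derives CL/f, honours nmol, converts to pmol, and does not notice the result. The formula itself names pmol, so a programmer aiming for those units could apply 295.7 directly and be right. This stands too, and is why the error is conditional.

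The slip might be on the other side of the equation, since 1 mg = 295.7 nmol also balances. That is correct, but it is the same factor of 1000 and leads to the same corrected statement. Nor can a misread character in the equation be excluded without the source PDF. Against that, pmol appears correctly twice in the same definition, and the sponsor can settle it by looking.

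Finally, because SAP 7.4 also gives the rate in µg/hr, weight is not strictly needed. That is true for that route. The conversion is nevertheless printed per kg, so the per-kg route should be usable as well.

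**Conclusion.** The point holds. The printed conversion is wrong by a factor of exactly 1000, and any CL/f obtained by following the printed unit is too large by that factor, whatever the dose or concentration. The conclusion rests on the formula's own units and the 29-residue description. It needs no outside molecular weight, and the residue-mass range is an assumption used only to confirm that pmol fits. The Css values are illustrative and do not affect the ratio.

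The consequence is confined to clearance, and only if it is derived with the printed unit. No efficacy or safety analysis is touched. It should be corrected because the defect is certain and the remedy is trivial, not because it threatens the trial's conclusions.

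**What to change.** In SAP 6.1.7:

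- Replace the conversion with 1 µg/kg/hr = 295.7 pmol/kg/h, and state the molecular weight from which it was calculated.
- Replace the stray mention of weight with the full step: R0 (pmol/h) = infusion rate (µg/kg/hr) × 295.7 × body weight (kg), or equivalently infusion rate (µg/hr) × 295.7. CL/f then comes out in L/h as stated.

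In SAP 11.1, name clearance among the planned PK summaries if it is to be reported. If it is not, delete the definition from 6.1.7.

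The cost is a one-line SAP correction. It needs no new data and changes no other analysis. If any clearance values have already been programmed, check which unit was used.

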8.3. Secondary Efficacy Analysis

The secondary efficacy analysis for this study includes the below summaries. These are continuous endpoints and will be summarized using descriptive statistics by study visit, treatment group, and treatment period (where applicable). No inference will be performed and missing data will not be imputed.

Analysis to be performed on subgroup of patients having gastrostomy or NG-tube at screening:

- Rate of gastric carbohydrate administrations (NG tube or gastrostomy) per week to treat hypoglycemia during Weeks 2-4 (Treatment Period 1) and Weeks 6-8 (Treatment Period 2)
- Total amount of gastric carbohydrates administered (g) (Gastrostomy or NG-tube) to treat hypoglycemia per week during Weeks 2-4 (Treatment Period 1). A graphic will be produced.
- Total amount of gastric carbohydrates administered (NG tube or gastrostomy) per week during Weeks 2-4 (Treatment Period 1).
- Amount of nightly (midnight to 6 am) gastric carbohydrates administered (NG tube or gastrostomy) per week during Weeks 2-4 (Treatment Period 1).

Analysis to be performed on whole population:

- CGM percent time in hypoglycemia (<70 mg/dL or 3.9 mmol/L) during Weeks 2-4 (Treatment Period 1) and Weeks 6-8 (Treatment Period 2).
- CGM-detected hypoglycemia episode rate, defined as number of episodes <70 mg/dL (3.9 mmol/L) for 15 minutes or more per week, during Weeks 2-4 (Treatment Period 1). A single CGM episode will be defined as up until 60 minutes from the start of the episode even if normoglycemia (>70 mg/dL) is not reached within this time. A new episode of hypoglycemia is to be reported when the next PG value below 70 mg/dL (3.9 mmol/L) is measured. Episodes will be derived by programming.
- SMPG-detected hypoglycemia episode rate, defined as number of episodes <70 mg/dL (3.9 mmol/L), during Weeks 6-8 (Treatment Period 2). A single SMPG episode will be defined as up until 60 minutes from the start of the episode even if normoglycemia (>70 mg/dL) is not reached within this time. A new episode of hypoglycemia is to be reported when the next PG value below 70 mg/dL (3.9 mmol/L) is measured, this will be reported in the corresponding CRF form. The analysis will be based on the hypoglycemia episodes reported in the eCRF.
- CGM-detected clinically significant hypoglycemia episodes, defined as number of episodes <54 mg/dL (3.0 mmol/L) for 15 minutes or more per week, during Weeks 6-8 (Treatment Period 2).

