9.8. Concomitant Medication

Concomitant medications will be coded using World Health Organization Drug Dictionary Enhanced (WHO-DDE) (Version September 01, 2018 or later) thesaurus.

Medications that started before first dose of dasiglucagon (dasiglucagon + SOC treatment group) or randomization (SOC only treatment group) will be considered prior medications if they were stopped before first dose of dasiglucagon/randomization. Any medications ongoing at start of trial will be considered to be concomitant medication ongoing at start. If a medication starts during the trial it will be considered as medication starting during the trial.

Concomitant Medication are described on the FAS according to randomized treatment.

Frequencies and percentages will be summarized descriptively by Anatomical Therapeutic Chemical (ATC) classification Level 4 and Preferred Name, if applicable, by overall patients and treatment group within treatment period. The summary will be presented in descending order of frequency of ATC and then Preferred Name within ATC based on overall patients.

10. Changes from Planned Analysis

- The protocol mentioned how to handle analyses involving trial site; however, since randomization is stratified by region (US vs non-US), region will be included in the analyses (it is not included in the protocol). Thus no analyses will be performed by trial site.
- The Full Analysis Set definition was clarified to indicate that the primary endpoint baseline assessment needs to be non-missing for a patient to be included in the set.
- A PK Set was added to support summaries of PK data.
- In the protocol a common methodology for the imputation of missing data for primary and key secondary endpoints was described. This has been split into appropriate methods for imputing missing event data based on the negative binomial model and non-event data based on the MCMC method for non-monotone missing data and sequential regression for monotone missing data.
- Baseline for endpoints related to external CGM data will be defined taking into account data from 14 days before randomization, those days will not necessary be consecutive, this is different from baseline definition of the other endpoints.

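### CGM-detected episode rates are divided by calendar weeks, so permitted sensor-off days count as episode-free and the on-treatment rates are understated

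*SAP*

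**What the plan says.** SAP 6.1.7 defines the event rate as the "average of the weekly number (sum) of events/episodes, based on the number of weeks in the relevant period", and the number of weeks as the "number of days in a relevant period (Baseline, Treatment Period 1, Week 2-4, Treatment Period 2, or Week 6-8) divided by 7". The only shortening it gives is for dropout: "If a subject discontinues during a week, then a partial week will be calculated". The study week that supplies the dates is "a 7- or 21-day period derived for displays of events related to CGM and/or SMPG results", with calendar start and stop dates, so it covers CGM events explicitly.

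Two endpoints in SAP 8.3 depend on this. One is the "CGM-detected hypoglycemia episode rate, defined as number of episodes <70 mg/dL (3.9 mmol/L) for 15 minutes or more per week, during Weeks 2-4". The other is the clinically significant version (<54 mg/dL) in Weeks 6-8. Both come from the sensor alone: "Episodes are defined by programming using external CGM data" (SAP 6.1.7).

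SAP 8, in its paragraph on continuous glucose monitoring, says "short pauses of 1-3 days due to skin irritation or discomfort are allowed after consultation with the investigator". The protocol's CGM section (10.2.1.2 in version 13.0, 11.2.1.2 in version 14.0) permits the same. Neither document limits the number of pauses.

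For the CGM baseline, SAP 10 says it "will be defined taking into account data from 14 days before randomization, those days will not necessary be consecutive" and notes that this departs from the baseline of the other endpoints. The study-week table in 6.1.7 lists Baseline as Days -14 to -1.

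SAP 8.3 presents observed values and change from baseline for both rates, without inference or imputation.

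**The concern.** A paused day adds nothing to the count of CGM episodes and a full day to the divisor. The rate thus treats time without observation as time without hypoglycemia. The SAP does not do this with its other CGM measures: percent time is taken over the minutes the sensor was worn, and the area over the glucose curve is divided by the duration of CGM assessment (both in 6.1.7). Only the episode rate keeps the calendar divisor.

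This matters because treatment is open-label and SMPG episodes are those entered in the eCRF, which depend on a caregiver testing and recording. The masked CGM episode count does not depend on that, so readers will look to it for corroboration. A rate that falls when the sensor comes off weakens that use. In Treatment Period 2 every child receives dasiglucagon, so the <54 mg/dL rate has no concurrent control and readers will lean on its change from baseline.

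**Working it through.** **Inputs.** Window dates, event rate and number of weeks: SAP 6.1.7. Pause length of 1-3 days: SAP 8. Five minutes per CGM reading: SAP 6.1.7. Assumptions: the true episode rate is constant, the same with the sensor on or off, and a paused day is a whole day without data.

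**1. The plan's own divisor.** Weeks 2-4 run from Day 8 to Day 28: 28 - 8 + 1 = 21 days, and 21/7 = 3 weeks. This agrees with the log(3) offset that SAP 8.1.1 uses for a full Weeks 2-4. Weeks 6-8 give 56 - 36 + 1 = 21 days, also 3 weeks.

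**2. Error in the on-treatment rate.** With true weekly rate L and d days off, the expected count is L x (21 - d)/7. Dividing by 3 gives L x (21 - d)/21, a relative error of -d/21. Within the one study week that holds the pause, the error is -d/7. Neither depends on L.

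| Days off in one pause | 21-day rate | Single-week display |
|---|---|---|
| 1 | -1/21 = -4.8% | -1/7 = -14.3% |
| 2 | -2/21 = -9.5% | -2/7 = -28.6% |
| 3 | -3/21 = -14.3% | -3/7 = -42.9% |

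Two full 3-day pauses would give -6/21 = -28.6%. The text allows this, but nothing shows that it occurs.

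**3. Illustration (assumed 10 episodes per week, one 3-day pause).** Expected count: 10 x 18/7 = 25.7. Calendar rate: 25.7/3 = 8.57. Rate on worn time: 25.7/(18/7) = 10.0. A Poisson simulation gave 8.57 for the calendar rate. Against a baseline of 10.00 the change was -1.42 with calendar weeks and +0.01 with worn time.

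**4. Change from baseline, no true change.**
- Baseline from 14 worn days: the change equals the error in step 2, always toward improvement.
- Baseline from 14 calendar days, 2 off, then 3 of 21 off: (18/21)/(12/14) - 1 = 0%.
- Baseline from 14 calendar days, 3 off, then 1 of 21 off: (20/21)/(11/14) - 1 = +21.2%, a false worsening.

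**5. Between arms, no true effect.** Three days off for every child in both arms gives a rate ratio of 18/18 = 1.00. In the dasiglucagon arm only, it is 18/21 = 0.857; in the SOC arm only, 21/18 = 1.167. If a proportion p of an arm has one 3-day pause, that arm's mean is off by p x 14.3%, so a 10% error needs p = 0.10/0.143 = 0.70.

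**The case against.** Days in the relevant period might be taken to mean days with CGM data. The text does not support that. Its one exception is discontinuation, and the study-week table fixes calendar start and stop dates. If worn days are meant, the SAP should say so.

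The objections to size and weight mostly stand. Pauses are described as short and need the investigator's involvement, and a single pause of 1 or 2 days costs less than 10% over 21 days. Both endpoints are descriptive. Percent time in range, percent time <70 mg/dL and both area measures also come from the masked sensor and are correctly scaled.

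A reader might infer that change from baseline must show a false improvement. The documents do not establish this. Non-consecutive baseline days suggest that gaps are skipped, but no readable sentence says the days are worn days. The text where SAP 6.1.1 (Baseline) would stand, and text directly after the CGM-baseline item in SAP 10, are not in the public copy and may settle it. Screening can be as short as 14 days, which leaves no spare days to replace a gap. Step 4 shows that the direction turns on this.

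A reader might also infer that dasiglucagon is favoured over SOC. Nothing in the documents says that wear differs between arms, and the bias could run either way. Nor is change from baseline the only view of Period 2: observed values are presented, and percent time <70 mg/dL in Weeks 6-8 is reported on worn time.

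**Conclusion.** The divisor is wrong as written for the two CGM-detected episode rates. Sensor-off days enter as episode-free, which understates a paused child's on-treatment rate by 4.8% to 14.3% per pause over 21 days and by up to 43% in a single-week display. These figures assume a constant rate and whole days off. The arm-level size cannot be stated without wear data.

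The effect on change from baseline is conditional: toward improvement if the baseline uses worn days, possibly nil or reversed if it uses calendar days. The understatement of the on-treatment rate does not depend on which is true. The between-arm contrast is biased only to the extent that wear differs.

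The consequences stop at two descriptive secondary endpoints. The primary endpoint, the key secondary endpoints, alpha and power are unaffected. The change is still worth making, because the error is systematic and cheap to remove.

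**What to change.** In SAP 6.1.7, for the CGM-detected and clinically significant CGM-detected episode rates only, replace the number of weeks by CGM observation time in weeks: number of non-missing CGM readings x 5 minutes / 10,080 (7 x 24 x 60 minutes). Use the same readings as the percent-time denominator, and apply the rule at Baseline, in each study week, in Weeks 2-4 and in Weeks 6-8. Using one rule at baseline and on treatment also removes the uncertainty about how the CGM baseline days are chosen. Report observation time by arm and period beside the rate. Keep calendar weeks for SMPG readings and gastric carbohydrate administrations.

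The cost is one sentence and a small programming change, since the reading counts are already needed for percent time. The drawback is that rates from children with very short wear become noisier. Either flag those children, or summarise each arm as total episodes divided by total observation time. The new rate still assumes that unobserved time resembles observed time.
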